6.2.5 Follow-up/Final Evaluations

Follow-up evaluations will consist of a 2-week telephone call, 6-week clinic visit, 9-week telephone call, 12-week clinic visit, and 24-week mail-in assessment:

2-Week Telephone Call

- Two weeks after the start of the yoga or control program, coordinators will call women to assess adverse events, address any concerns, and reinforce adherence to group classes and home practice of yoga or stretching/strengthening exercises.
- Adherence to and challenges in performing usual behavioral self-management strategies for incontinence will also be assessed.
- Women will be reminded to continue recording home yoga or stretching/strengthening practice in their practice logs and return their logs each week to the yoga class instructors. They will also be reminded to start filling out a second voiding diary 3 days before the 6-Week Clinic Visit.

6-Week Clinic Visit

- Six weeks after the start of the yoga or control program, women will return for a follow-up visit, bringing their second completed voiding diary.
- Voiding diaries will be retrieved by the research coordinator and delivered to a blinded analyst for data abstraction.
- Adverse events will be recorded using standardized forms (see safety monitoring section).
- Adherence to yoga or stretching/strengthening practice and incontinence self-management strategies will be re-assessed.
- Yoga and stretching/strengthening self-efficacy questionnaire measures will be administered.
- Participants will re-self-administer questionnaires about incontinence-related quality of life, depression and anxiety symptoms, and sleep quality.
- Participants will be asked about their use of other strategies to manage their incontinence.
- Physical function will be assessed by questionnaire as well as direct physical performance testing.
- Current use of prescription and over-the-counter medications will be re-reviewed.
- Women will be given a third voiding diary to complete before the 12-week visit, and the 12-week visit will be scheduled.

9-Week Telephone Call

- Nine weeks after the start of the yoga or control program, coordinators will call women to assess adverse events, address any concerns, and reinforce adherence to group classes and home practice of yoga or stretching/strengthening exercises.
- Adherence to and challenges in performing usual behavioral self-management strategies for incontinence will also be assessed.
- Women will be reminded to continue recording home yoga or stretching/strengthening practice in their practice logs and return their logs each week to the yoga class instructors. They will also be reminded to start filling out a third voiding diary 3 days before the 12-Week Clinic Visit.

12-Week Clinic Visit

- Twelve weeks after the start of the yoga or control program, women will return for another clinic visit, bringing their third completed voiding diary.
- Voiding diaries will be retrieved by the research coordinator and delivered to a blinded analyst for data abstraction.
- Adverse events will be recorded using standardized forms (see safety monitoring section).
- Yoga and stretching/strengthening self-efficacy questionnaire measures will be re-administered.
- Participants will re-self-administer questionnaires about incontinence-related quality of life, depression and anxiety symptoms, and sleep quality.
- Physical function will be re-assessed by questionnaire as well as by physical performance testing.
- Participants will be asked about their use of other strategies to manage their incontinence.
- Cardiac autonomic function will be assessed through heart rate variability and impedance cardiography measurements.
- Participants will be invited to undergo pelvic floor muscle strength assessments. The assessment may be performed directly during the 12-Week Clinic Visit, or an alternate clinic assessment may be scheduled specifically for this exam.
- Current use of prescription and over-the-counter medications will be re-reviewed.
- A satisfaction questionnaire will be administered to assess overall satisfaction with study procedures and change in incontinence symptoms.
- Women will be encouraged to continue practicing yoga or stretching/strengthening exercises for at least two hours per week for the next 12 weeks and record this practice in their home practice logs.
- As an optional activity, selected participants in the yoga arm may be invited to take part in brief qualitative interviews to discuss their barriers and facilitators to learning and maintaining practice of yoga after this visit.

24-Week (a.k.a. 3-Month Post-Intervention) Assessment

- Approximately twelve weeks after completion of the intervention programs, coordinators will call participants to them to complete their fourth voiding diary at home (the blank diary will be mailed in advance to participants at home, and participants will return it using a pre-stamped and addressed envelope).
- Adverse events will be assessed by telephone, video, or in-person visit and recorded using standardized forms (see safety monitoring section).
- Women will also be asked to complete questionnaires addressing symptom, quality-of life, and sleep outcomes as well as yoga or stretching/strengthening practice adherence and self-efficacy at home (questionnaires will be mailed in advance to participants at home, or can be completed via an on-line survey).
- Participants will be asked about their continued practice of yoga or stretching/strengthening techniques and their use of other strategies to manage their incontinence.
- Participants will be asked to mail back home practice diaries documenting their continued practice of yoga or stretching/strengthening techniques.
- Women will be encouraged continue practicing yoga or stretching/strengthening exercises for at least two hours per week for the next 12 weeks and record this practice in their home practice logs.

36-Week (a.k.a. 6-Month Post-Intervention) Assessment

- Approximately 24 weeks after completion of the yoga or control program, coordinators will call participants to them to complete their fifth voiding diary at home (the blank diary will be mailed in advance to participants at home).
- Adverse events will be assessed by telephone, video, or in-person visit and recorded using standardized forms (see safety monitoring section).
- Women will also be asked to complete questionnaires addressing symptom, quality-of life, and sleep outcomes as well as yoga or stretching/strengthening practice adherence and self-efficacy at home (questionnaires will be mailed in advance to participants at home, or can be completed via an on-line survey).
- Participants will be asked about their continued practice of yoga or stretching/strengthening techniques and their use of other strategies to manage their incontinence.
- Participants will be asked to mail back home practice diaries documenting their continued practice of yoga or stretching/strengthening techniques.
- Women will also be asked to complete a close-out satisfaction questionnaire addressing their overall satisfaction with study procedures and change in incontinence symptoms (questionnaires will be mailed in advance to participants at home, or can be completed via an on-line survey).

Recommended time windows for completion each of the post-randomization follow-up evaluations will be as follows:

Follow-Up Assessment	Time Window
2-week telephone call	8 to 20 days after the start of the yoga or physical conditioning program
6-week clinic visit	36 to 48 days (i.e., 6 weeks +/- 6 days) after

	the start of the yoga or physical conditioning program
9-week telephone call	57 to 69 days after the start of the yoga therapy or physical conditioning program
12-week clinic visit	78 to 90 days (i.e., 12 weeks +/- 6 days) after the start of the yoga or physical conditioning program
24-week (i.e., 12-week post-intervention) telephone and mail-in assessment	Within 189 days (27 weeks) of the start of the yoga or stretching/strengthening program (allowing time for return of mail-in packet)
36-week (i.e., 24-week post-intervention) telephone and mail-in assessment	Within 273 days (39 weeks) of the start of the yoga or stretching/strengthening program (allowing time for return of mail-in packet)

6.2.6 Early Termination (also see section below)

If a participant indicates that she needs or wishes to discontinue all participation in the study, then she will be encouraged to complete an Early Termination visit. This visit will include as many of the procedures originally scheduled to take place at the 12-Week Clinic Visit as possible, including: assessment of adverse events; re-administration of questionnaires about condition-specific quality of life, depression and anxiety symptoms, and yoga or stretching/strengthening self-efficacy; review of current medications; re-assessment of weight, blood pressure, and heart rate; re-assessment of physical function, autonomic function, and pelvic floor strength; and administration of a study satisfaction questionnaire. The participant's reasons for terminating participation early will be explored and documented in her file.

Of note, a participant can discontinue participation in study intervention classes or intervention home practice without discontinuing participation in the overall study. When possible, participants who decide to stop attending or engaging in the study intervention programs will be asked to provide data at originally planned outcome assessment timepoints (e.g., at 12 weeks and at 12 and 24 weeks after the originally planned end of the intervention program). In this case, no early termination visit will be performed, but planned outcome assessment visits will be completed.

.

6.2.7 Table of Measures and Procedures

Summary of Measures and Procedures at Study Visits									
	Screening Phone Call	Screening Clinic Visit	Baseline Clinic Visit	Randomization Phone Call	2/9-Week Phone Call	6-Week Clinic Visit	12-Week Clinic Visit	12 week post-intervention	24-week post-intervention
Brief telephone screening interview	X								
Informed consent		X							
Demographic/medical history questionnaires		X							
Health-related habits questionnaires		X							
Review of current medications	X					X	X	X	X
Basic physical mobility testing	X								
Height, weight, blood pressure, and pulse	X						X		
Urine dipstick testing		X							
Urine pregnancy testing (if appropriate)	X								
Fluid intake and behavior questionnaire			X			X	X	X	X
Voiding diary return and review			X			X	X	X	X
Review of eligibility and randomization		X*	X*						
Incontinence self-management pamphlet		X							
Assessment of credibility/expectations of treatment				X					
Incontinence Impact Questionnaire			X			X	X	X	X
Urogenital Distress Inventory-6			X			X	X	X	X
Patient Perception of Bladder Condition			X			X	X	X	X
PISQ-IR Sexual Function Questionnaire			X			X	X	X	X
Center for Epidemiologic Studies Depression Scale			X			X	X	X	X
Spielberg State-Trait Anxiety Inventory			X			X	X	X	X
Hospital Anxiety and Depression Scale			X			X	X	X	X
Perceived Stress Scale			X			X	X	X	X
Pittsburg Sleep Quality Index			X			X	X	X	X
Perceived physical function assessment			X			X	X	X	X
Physical performance testing			X			X	X		
Autonomic measures (RSA and PEP)			X				X		
Pelvic floor muscle strength assessment			X				X		
Adverse events assessment					X	X	X	X	X
Yoga/stretching posture/exercise self-efficacy				X		X	X		
Yoga/stretching practice self-efficacy questionnaires				X		X	X	X	X
Assessment of co-interventions						X	X	X	X
Satisfaction/close-out questionnaire							X		X

*Randomization will take place at either the Baseline Clinic Visit or the Randomization Phone Call

7. SAFETY ASSESSMENTS

7.1 Potential Risks and Protective Measures

Although participation in this study is not expected to place participants at substantial risk of harm, study procedures may be associated with the following risks:

- **Yoga Intervention:** Possible risks associated with group yoga instruction and home yoga practice include muscle soreness and muscle/ligament strain, or other musculoskeletal injury if participants fall or lose their balance while trying to practice yoga poses.
- **Stretching/Strengthening Control Intervention:** Similar to the yoga intervention, possible risks associated with the stretching/strengthening control intervention include muscle soreness and muscle/ligament strain, or musculoskeletal injury if participants fall or lose their balance while trying to learn or practice the stretching or strengthening exercises.
- **Behavioral Incontinence Self-Management Pamphlet:** Provision of standard written information on usual first-line behavioral self-management strategies for incontinence such as pelvic floor muscle exercises and timed urination should not pose any risks to participants, although participants may find it inconvenient or unpleasant to read the pamphlet.
- **Questionnaires and Diaries:** Although the information participants provide on data collection forms and diaries is confidential, some participants may feel embarrassed at having to answer questions, especially those related to urinary symptoms, depression, anxiety, or sexual function. There will be slight inconvenience in time and effort to complete diaries and questionnaires.
- **Physical Exam Measurements:** There are no direct risks associated with undergoing measurement of height, weight, blood pressure, or heart rate, although participants may experience this as inconvenient or unpleasant.
- **Digital Pelvic Examination:** Digital pelvic examination (not requiring a speculum) and assessment of pelvic floor muscle strength may be associated with discomfort or soreness in the perineal or vaginal area, emotional reaction to being touched in the genital area, feeling of fullness or pressure in the rectum, or urge to urinate during or following the exam.
- **Perineometer Assessment:** Similar to digital pelvic exam, perineometer assessments of pelvic floor muscle strength (at the Stanford site only) may be associated with discomfort or soreness in the perineal or vaginal area, emotional reaction to being touched in the genital area, feeling of fullness or pressure in the rectum, or urge to urinate during or following the exam.
- **Urinalysis and Urine Pregnancy Testing:** There are no direct risks associated with collection of the clean-catch urine sample, although some participants may experience this as inconvenient or unpleasant.
- **Heart Rate Variability and Impedance Cardiography:** Heart rate variability and impedance cardiography will be obtained using a non-invasive Biopac electronic monitoring system. The only adverse effect that may result from these measurements is mild skin irritation at the site of the ECG or cardiac impedance

electrodes, which should disappear within 24 hours of removing the electrodes. Although noninvasive, measurement of heart rate variability and pre-ejection period may be experienced by participants as inconvenient or mildly unpleasant.

To minimize potential risks to participants associated with study interventions and procedures, the following steps will be taken:

- **Yoga Intervention:** The instructors leading the group yoga classes will be trained yoga teachers who will have experience in teaching adults from a wide range of ages to learn and practice yoga safely and will undergo specific, in-person training by the study's yoga expert consultants. The study protocol incorporates yoga props such as blocks and blankets to help participants perform yoga postures in such a way that will minimize the likelihood of muscle strain or musculoskeletal injury. The yoga instruction manuals and audio recordings are designed to include explicit tips on modifying or adapting postures to accommodate problems with mobility, flexibility, or balance.
- **Stretching/Strengthening Intervention:** Instruction for the control intervention classes will be provided by trained physical therapists or personal trainers who are experienced in teaching patients of all ages to perform physical exercises safely, and who will have completed in-person training with co-investigator [name], PT. Stretching and strengthening exercises have been selected to be appropriate for middle-aged and older women who may have flexibility or mobility limitations in addition to incontinence.
- **Behavioral Incontinence Self-Management Pamphlet:** The pamphlet used in this trial has previously been administered and refined in other large-scale research studies. Study coordinators will be available to answer participants' questions about the pamphlet if they arise.
- **Questionnaires and Diaries:** Any paper-based questionnaires or diaries collected in this research will be stored in a locked file cabinet in a locked room in research facilities, and data obtained from diaries and questionnaires will be stored on password-secured servers. All study staff are fully trained in good clinical practice and Human Subject Projections procedures, and the importance of participant confidentiality will be emphasized.
- **Physical Examination Measures:** Study coordinators who are responsible for obtaining physical exam measures will have prior clinical experience with performing physical exam measurements in middle-aged and older women, and will receive study-specific training to ensure that they perform measurements in a manner that is sensitive and minimizes discomfort to participants.
- **Digital Pelvic Examination:** Digital pelvic exams and assessment of pelvic floor muscle strength will be performed by clinically-trained consultants who have experience performing pelvic exams for clinical care and are trained to perform exams in a manner that is sensitive and minimizes discomfort to participants. Participants will be informed that they can ask to stop the exam for any reason; they can also decline the pelvic exam but take part in other aspects of the study.
- **Perineometer Assessment:** Perineometer-based assessment of pelvic floor muscle strength (at the Stanford site only) will be performed by a board-certified urogynecologist with experience performing pelvic exams for clinical care, experience in perineometry measurements, and training in performing exams in a manner that is sensitive and minimizes discomfort to participants. Participants

will be informed that they can ask to stop the assessment for any reason; they can also decline the pelvic exam but take part in other aspects of the study.

- **Urinalysis and Pregnancy Testing:** Study coordinators who are responsible for performing urine testing will be trained to instruct participants on providing urine samples in a manner that is sensitive and minimizes embarrassment.
- **Heart Rate Variability and Impedance Cardiography:** Participants with a history of allergy or adverse reaction to ECG electrodes or adhesives may to forgo undergo heart rate variability or impedance cardiography measures. If participants develop a skin reaction after testing is begun, measurements will be discontinued, and no further testing will be performed at any future visits.

7.2 Methods and Timing of Safety Assessments

To monitor participant safety, a clinical coordinator will assess for adverse events at each follow-up telephone and in-person contact following randomization, starting with the 2-Week Telephone Call. Additionally, participants will be given telephone numbers to call study staff in between scheduled study visits or calls to report any significant health changes.

Coordinators will not prompt participants to provide information about specific types of adverse events at follow-up visits, but instead encourage participants to volunteer information by asking the standardized, open-ended question, “Have there been any changes in your health since your last visit?” Any negative changes in health reported by participants will then be recorded on standardized AE or SAE forms, as appropriate (see below for definitions and documentation).

7.3 Adverse Events and Serious Adverse Events

7.3.1 AE/SAE Definitions

An Adverse Event (AE) is any untoward medical occurrence in participant that occurs during the study or with use of the study interventions. An adverse finding can include a sign, symptom, abnormal assessment, or any combination of these. Medical conditions or diseases present before starting study interventions will only be considered adverse events if they worsen after starting the intervention.

A Serious Adverse Event (SAE) is any AE that results in death, a life-threatening event, inpatient hospitalization or prolongation of existing hospitalization, a persistent or significant disability/incapacity, a congenital anomaly or birth defect, or any other important medical event that jeopardizes the safety of participants based upon appropriate medical judgment.

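### Section 7.3.1 contradicts itself on events between consent and the start of the intervention, and no adverse-event question covers the baseline pelvic and electrode tests until 8 to about 96 days later

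*Combined protocol and SAP*

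**What the plan says.** **Definition.** Section 7.3.1 begins broadly: "An Adverse Event (AE) is any untoward medical occurrence in participant that occurs during the study or with use of the study interventions". It adds that a sign or symptom can qualify. It closes with a restriction: "Medical conditions or diseases present before starting study interventions will only be considered adverse events if they worsen after starting the intervention".

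**Timing of enquiry.** Under Section 7.2 a coordinator will "assess for adverse events at each follow-up telephone and in-person contact following randomization, starting with the 2-Week Telephone Call". The table in Section 6.2.7 agrees: the adverse-event row has no mark at the Baseline Clinic Visit or the Randomization Phone Call. Section 6.2.5 sets the window for the 2-week call at "8 to 20 days after the start of the yoga or physical conditioning program".

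**Tests before that point.** Consent is signed at the start of the Screening Clinic Visit (6.2.2). The digital pelvic exam, perineometry at Stanford, the heart rate variability and impedance recordings, and the physical performance tests belong to the Baseline Clinic Visit (6.2.3). The pelvic assessment may have its own appointment.

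**Named harms.** Section 7.1 says of both the digital exam and perineometry that they "may be associated with discomfort or soreness in the perineal or vaginal area", and also lists emotional reaction, rectal pressure and urge to urinate. For the electrode recordings: "The only adverse effect that may result from these measurements is mild skin irritation", expected to clear within 24 hours. It lists no harm for the performance tests.

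**Other rules.** Section 7.3.2 has every negative health change that a participant reports put on a form. Section 7.4.2 provides for non-serious events linked to procedures as well as interventions. Section 7.6 asks the Data and Safety Monitor to consider how adverse events relate to study procedures.

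**The concern.** Two separate defects meet in the interval between consent and the first class.

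The first is in the definition. A condition caused by a baseline test and still present when classes begin satisfies the opening sentence of 7.3.1. The closing sentence removes it unless it then worsens. Two coordinators could classify the same event differently, each with textual support.

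The second is in the schedule. The plan names harms of the baseline pelvic and electrode tests but schedules no question soon enough to catch them while they are present. A woman who has the tests and is not randomized, for example because she is no longer available when the deferred randomization call is made, is never asked on schedule.

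At stake is how far the trial's record of procedure-related harm can be relied on, and what the Data and Safety Monitor has to work from when judging it. A low count from the baseline tests would partly reflect when the question was asked.

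**Working it through.** The plan states no figure on this point, so there is none to reproduce. The check is one of timing and one of text.

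**Timing.** Lag from baseline tests to first scheduled question = a + b + c, where:
- a = Baseline Clinic Visit to randomization. It is 0 if done at that visit. Otherwise it is ideally within 1 month and never more than 2 months after screening is complete (6.2.4). I take the Baseline Clinic Visit as the last screening step, following 6.2.1.
- b = randomization to program start, 0 to 14 days (6.2.4). Section 4.3 counts the two weeks from the orientation session instead; I treat the two as the same date.
- c = program start to the 2-week call, 8 to 20 days (6.2.5), which is 14 ± 6.

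| Case | Sum | Lag in days |
|---|---|---|
| Randomized at the Baseline Clinic Visit, shortest | 0 + 0 + 8 | 8 |
| Randomized at the Baseline Clinic Visit, longest | 0 + 14 + 20 | 34 |
| Deferred to a call, shortest (visit at least 15 days before start, so a + b ≥ 15) | 15 + 8 | 23 |
| Deferred, at the ideal 1-month limit | (28 to 31) + 14 + 20 | 62 to 65 |
| Deferred, at the 2-month limit | (59 to 62) + 14 + 20 | 93 to 96 |

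The range is 8 to about 96 days. Electrode irritation, expected to last under 24 hours, will normally have gone before even the earliest scheduled question on day 8. For a pelvic exam held at a separate appointment the lag may differ.

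**Text.** Take a condition that a baseline test causes, that is still present when classes begin, and that does not worsen afterwards.
- 7.3.1, opening sentence: included, because it arose after consent and during the study.
- 7.3.1, closing sentence, read literally: excluded, because it was present before the intervention and did not worsen.
- 7.3.2: recorded, if the participant reports it.
- 7.4.2: covered by the reporting rule, if it may pose substantial risk and is potentially linked to a procedure.
- 7.6: within what the Data and Safety Monitor is asked to judge.

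The closing sentence is the only one of the five that removes it.

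**The case against.** The strongest reply is that the closing sentence of 7.3.1 is an ordinary clause for pre-existing illness. It speaks of conditions and diseases, whereas the harms in 7.1 are mostly passing symptoms, and 7.3.1 itself lets a symptom count. Nor is the plan silent in the interval. Participants have a number to call, the open question looks back to the last visit, electrode testing stops if a skin reaction appears, and trained clinicians perform the pelvic tests.

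Much of this stands, and it rules out several stronger readings:
- That the definition itself begins after baseline. Its opening sentence covers the whole study.
- That baseline-test harms are excluded by rule. That is one literal reading, and it fits a lasting condition better than transient soreness.
- That the plan names harms for the performance tests. It names none.
- That all of the roughly 240 randomized women are exposed to the tests with named harms. The pelvic exam and perineometry are optional, perineometry is at one site only, and the autonomic measures could be declined during the pandemic (6.1.6, 6.1.7).
- That a further gap of 78 to 111 days follows the 12-week tests (168 − 90 to 189 − 78). This takes the order of bullets in 6.2.5 as the order of procedures and assumes that the next contact is no earlier than day 168. The plan does allow that "The assessment may be performed directly during the 12-Week Clinic Visit, or an alternate clinic assessment may be scheduled specifically for this exam", but a separate exam is an in-person contact after randomization, which 7.2 already covers.
- That the trial will report its procedures as nearly harmless. No passage says so, and procedure harm rates are not an objective.

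The safeguards still leave a gap. The call-in route asks for significant changes, a threshold that mild soreness or distress may not meet. The look-back question is unprompted and may come months later. The instruction to stop electrode testing mentions no adverse-event form. None of these supplies a scheduled question for women who are never randomized.

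**Conclusion.** The point holds as a conflict in the text and a gap in scheduled collection. Section 7.3.1 disagrees with itself and with 7.3.2, 7.4.2 and 7.6 about events between consent and the start of the intervention. The first scheduled question comes 8 to about 96 days after the baseline pelvic and electrode tests, and never for women tested but not randomized. The documents do not say how many such women to expect.

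The upper figure assumes that the 2-month limit runs from the Baseline Clinic Visit and that every window is used in full. At the 1-month ideal the maximum is 62 to 65 days.

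The consequence is limited. The named harms are mostly mild and transient, and what suffers is reporting of procedure safety. The efficacy analysis is untouched. So is the between-arm comparison of intervention harms, because the baseline tests precede the intervention. The change is worth making because it is cheap and removes an ambiguity in a core safety definition.

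**What to change.** 1. Reword the last sentence of 7.3.1 so that a condition counts as pre-existing only if it was present before the first study procedure after consent, and becomes an adverse event if it worsens after that procedure.
2. In 7.2 and the table in 6.2.7, start adverse-event collection at the Baseline Clinic Visit.
3. Have a coordinator ask the existing open-ended question at the end of the baseline test session, including a separately scheduled pelvic exam, and again at randomization.
4. At 12 weeks, state that the question comes after the tests. The pelvic assessor, who is blinded after randomization (6.1.7), should not be the one to ask it, since the answer could reveal the assignment.
5. Tabulate pre-intervention events separately, so that the comparison between arms keeps its present starting point.

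The cost is protocol wording, a line on existing forms, about a minute per session and a few more recorded mild events.
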